7 RESEARCH METHODS

7.1 Study Design

The proposed study will be an observational (non-experimental), nationwide, register-based study using data from the Nordic national population registers. The associations between current DL use and seizures, current DL use and SVT, and current DL use and A-fib/flu will be assessed in analyses using person-specific linkage of data (Table 1). The cohort of all DL users will be used for describing DL use (Substudy 1). The cohorts of individuals who have had first seizure, SVT, or A-fib/flu will be used to examine the IRs of first seizure, SVT, and A-fib/flu in the general population (Substudies 2A, 3A, and 4A, respectively). A cohort study design among all DL users (i.e. a risk interval design including the DL-only cohort [Glanz, J. M., et al 2006]) will be used for the association between current DL exposure and first seizure, SVT, and A-fib/flu (Substudies 2B, 3B, and 4B, respectively).

Table 1 Overview of Substudies.

Primary objectives	
Substudy	Aim
1	Descriptive analysis of DL use in the general population
2A	Descriptive analysis of IR of first seizure in the general population
2B	Association between DL exposure and risk of first seizure
3A	Descriptive analysis of IR of first SVT in the general population
3B	Association between DL exposure and risk of first SVT
4A	Descriptive analysis of IR of first A-fib/flu in general population
4B	Association between DL exposure and risk of A-fib/flu

Pharmacoepidemiological studies typically use dispensed days' supply as a surrogate for current drug exposure, assuming they are used every day. However, in contrast to medications for many chronic diseases, antihistamines may be used intermittently, as needed for symptoms. For the main analyses in the present study of the association between current DL use and outcomes of interest (Substudies 2B, 3B, and 4B), person time exposed to DL will be determined from dispensing records. "Current use" (i.e., "exposed" period) will be defined for each prescription as the sum of days' supply plus a 4 week grace period to account for intermittent use and a possible wash-out effect. If a new DL prescription redemption occurs during an exposed period (either during the period equal to the sum of the days' supply or the 4 week grace period), the exposure period extends from that date with a period equal to the sum of days' supply in the newly redeemed prescription plus a 4 week grace period. Note: Days' supply will be calculated from the quantity of tablets or amount of solution dispensed and the standard daily dose based on the age of the patient (i.e., 6-11 months: 1 mg/day; 12 months-5 years: 1.25 mg/day; 6-11 years: 2.5 mg/day; ≥ 12 years: 5 mg/day). Because the drug is used "as needed", it is quite possible that there may still be exposed days in the period after the latest exposed period (i.e., after the exposed period that includes the sum of the days' supply plus a 4 week grace period). To minimize exposure misclassification, we propose to use person time at least 26 weeks beyond the dispensing date of the prior prescription as the "unexposed" reference period. The "unexposed" period is actually a period with remote exposure to DL because dispensing of DL is a condition of entering the study population. We will refer to the "remote exposure" period as "unexposed" (For more details, see section 7.3.1 and [Figure 1](#)). The time between the exposed period and the unexposed period is considered neither exposed nor unexposed.

The advantage of using this design restricted to DL users, in which the same persons may have both exposed and unexposed periods, is that we reduce confounding due to time-independent factors associated with DL use.

The study is divided into six parts described below (For more details, see section 7.7).

1. Substudy 1

A descriptive analysis of DL use in the general population. To describe DL use in the general population, we will identify both prevalent and incident users of DL and describe the distribution of the number of redeemed DL prescriptions for the total population and stratified by country, age, sex, calendar year, seasonality, severity of rhinitis, asthmatic status, and chronic urticaria status.

2. Substudies 2A and 2B

A descriptive analysis of the IR of first seizure overall in the general population and stratified by country, sex, and age will be conducted (2A).

Among persons ever dispensed DL, the association between exposure to DL use and first seizure will be evaluated using Poisson regression of the IR of first seizure for the total population and stratified by age when accounting for confounding factors (2B).

3. Substudies 3A and 3B

Descriptive analysis of the IR of SVT overall in the general population and stratified by country, sex, and age will be conducted (3A).

Among persons ever dispensed DL, the association between exposure to DL use and first SVT will be evaluated using Poisson regression of the IR of first SVT for the total population and stratified by age when accounting for confounding factors (3B).

4. Substudies 4A and 4B

Descriptive analysis of the IR of A-fib/flu overall in the general population and stratified by country, sex, and age will be conducted (4A).

Among persons ever dispensed DL, the association between exposure to DL use and first A-fib/flu will be evaluated using Poisson regression of the IR of first A-fib/flu for the total population and stratified by age when accounting for confounding factors (4B).

5. Supplementary analyses

In total, 10 supplementary analyses will be performed to examine the robustness of the results. These are described in further details in section 7.7.6 of the protocol as well as in the SAP.

7.2 **Setting**

The cohort of individuals with redeemed DL prescriptions will be identified from the four Nordic national prescription registers. Similarly, the cohort of all individuals with seizures (first seizure), the cohort of individuals with SVT, and the cohort of individuals with A-fib/flu will be identified from the four Nordic national patient registers. The population is comprised of all individuals with DL prescriptions and of all individuals with seizures, SVT, or A-fib/flu in the four Nordic countries in the period 2001–2015 in Denmark and Finland, 2008–2015 in Norway, and July 2005–2015 in Sweden (Table 5). Individuals for Substudies 2B, 3B, and 4B become eligible for the study cohort upon first dispensing of DL (See sections 7.2.1 and 7.2.2). Data will be available until and including 2015 for all countries.

7.2.1 Inclusion criteria

Substudy 1

- Individuals who have redeemed at least one prescription of DL during the study period (DL cohort) and have residential location in Denmark, Finland, Norway, or Sweden.
- General population living in Denmark, Finland, Norway, and Sweden on 01 January of each year.

Substudy 2A

- Individuals who have experienced a seizure during the study period (seizure cohort) and have residential location in Denmark, Finland, Norway, or Sweden.
- General population living in Denmark, Finland, Norway, and Sweden on 01 January of each year.

Substudy 2B

- Individuals who have redeemed at least one prescription of DL during the study period (DL cohort) and have residential location in Denmark, Finland, Norway, or Sweden.

Substudy 3A

- Individuals who have experienced a SVT during the study period (SVT cohort) and have residential location in Denmark, Finland, Norway, or Sweden.
- General population living in Denmark, Finland, Norway, and Sweden on 01 January of each year.

Substudy 3B

- Individuals who have redeemed at least one prescription of DL during the study period (DL cohort) and have residential location in Denmark, Finland, Norway, or Sweden.

Substudy 4A

- Individuals who have had an A-fib/flu diagnosis during the study period (A-fib/flu cohort) and have residential location in Denmark, Finland, Norway, or Sweden.

- General population living in Denmark, Finland, Norway, and Sweden on 01 January of each year.

Substudy 4B

- Individuals who have redeemed at least one prescription of DL during the study period (DL cohort) and have residential location in Denmark, Finland, Norway, or Sweden.

7.2.2 Exclusion criteria

Substudy 2A

- Individuals with a diagnosis of seizure, epilepsy, or prescriptions of antiepileptic medicine before entering the study period, as they have prevalent disease.
- Individuals with a diagnosis of malignant brain tumor or head trauma before the first seizure, as they are at high risk of seizures due to causes other than DL use.

Substudy 2B

- Individuals with a diagnosis of seizures, epilepsy, prescriptions of antiepileptic medicine, malignant brain tumor, or head trauma before redemption of first DL prescription, as they have prevalent disease or are at high risk of seizures due to causes other than DL use.
- Individuals with a brain tumor (benign and malignant), initiation of treatment with antiepileptic medicine, or head trauma occurring after beginning of DL use will be censored at date of first occurrence, as they are at high risk of seizures due to causes other than DL use.

Substudies 3A and 4A

- Individuals with a diagnosis of SVT or A-fib/flu before entering the study period, as they have prevalent disease.
- Individuals with a diagnosis of congenital pre-excitation syndrome (e.g., Wolff Parkinson White) before entering the study period, as they are at high risk of cardiac SVT or A-fib/flu due to causes other than DL use.

Substudies 3B and 4B

- Individuals with a diagnosis of SVT or A-fib/flu before use of DL, as they have prevalent disease.
- Individuals with a diagnosis of congenital pre-excitation syndrome (e.g., Wolff Parkinson White) before use of DL, as they are at high risk of SVT or A-fib/flu due to causes other than DL.

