7.4 Data Sources

The DL study will include register information from four Nordic countries – Denmark, Finland, Norway, and Sweden. In addition to a long history of collecting high quality information on births, deaths, immigration and emigration, disease incidence, and activities in the healthcare sector [Thygesen, L., et al 2011], exceptional opportunities to perform register-based research are driven by the unique PIC introduced in the Nordic countries in the 1960's and available to all persons with permanent residence in the Nordic countries [Pedersen, C. B. 2011]. The PIC makes it possible to link information at the individual level from several registers for scientific research purposes. The national prescription registers and national patient registers within each of the Nordic countries capture all the individual encounters of purchasing prescribed DL and allow sufficient longitudinal data to differentiate between first and recurrent seizures, as only first seizure will be analyzed, and to identify incident SVT and A-fib/flu cases. Person-specific use of DL will be elucidated from the

national prescription registers by obtaining information on redemption of DL prescription for each person [Furu, K., et al 2009]. Person-specific information on seizures, SVT, and A-fib/flu will be derived from the Nordic national patient registers.

Table 5 presents key information on the population-based health registers in the Nordic countries of relevance for the present study. Data will be available until and including 2015 for all countries. The data extraction period refers to the longest period for which data on exclusion variables (e.g., seizures, SVT, or A-fib/flu before baseline) can be obtained for.

Table 5 Overview of national health registers in the Nordic countries of relevance for the present study.

Register	Country			
	Denmark	Finland	Norway	Sweden
National prescription register	1995–2015	1994–2015	2004–2015	2005–2015
National patient register	1977–2015 (1)	1967–2015 (2)	2008–2015	1987–2015 (3)
Civil registration system	1968–2015	1967–2015	1964–2015	1965–2015
Study period	2001–2015 (15 years)	2001–2015 (15 years)	2008–2015 (8 years)	July 2005–2015 (11 years)
Data extraction period	1977–2015	1967–2015	2008–2015	1987–2015

(1) Contacts with outpatient clinics (incl. emergency departments) since 1995.

(2) Contacts with outpatient clinics (incl. emergency departments) since 1998.

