7.7.2 Substudy 2: First seizure

Substudy 2A

A cohort study estimating the incidence of first seizures in the general population will be conducted. The cohort of individuals with seizures and the distribution of the population by age, year, and country will be used to derive estimates for the general population. The number of individuals in the general population on 01 January of each year will be obtained from the NORDCAN database and used as an estimate of the number of person years at risk assuming each person in the population on 01 January of each year contributes one person year at risk [Association of Nordic Cancer Registries 2009]. The IRs of seizure will be shown for the total population and stratified by country, sex, and age. The 95% confidence interval for IRs will be calculated as:

$$\dots / \exp(1.96/\sqrt{N_{new\ users}}) \text{ to } IR * \exp(1.96/\sqrt{N_{new\ users}})$$

where IR is the incidence rate, exp is the exponential function, and $N_{new\ users}$ is the number of new users [Kirkwood, B. R. 2003].

Substudy 2B

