- Left-truncation is a potential bias in the study meaning that we have no information on DL use before the start of registration of prescriptions in each country. Left-truncation bias in relation to DL use is only a relevant issue for Sweden and Norway since DL was available from 2001, but the prescription registers in Norway and Sweden were established in 2004 and 2005, respectively (Table 4). Therefore, we do not know whether a DL user in the first year of registration in Norway and Sweden is a long-term user (prevalent user) or a first-time user (incident user). To account for this potential bias, a person with prescription redemption of DL in Norway and Sweden within the first 6 months after establishment of the prescriptions registers will not be included. This is not a limitation in Denmark and Finland since DL was first approved in 2001 and the prescription registers in Denmark and Finland were established in 1995 and 1994, respectively. However, left-truncation bias might also occur when persons are immigrating into the study population. Therefore we also exclude persons with DL prescription redemptions within 6 months after immigrating to Denmark, Finland, Norway, or Sweden.
- There is a possibility that patients could purchase DL over-the-counter; however, because of reimbursement systems in the Nordic countries, it is actually less expensive to purchase prescription DL. In Norway and Sweden DL has only been allowed for prescription sale; However, in Denmark, DL has been available for over-the-counter sale since 2013, but over-the-counter sales only counted for less than 4 % of the total amount of DL purchased in 2013. A supplementary analysis will examine the associations under consideration restricting the time period to include only years where DL was not allowed for OTC sale.
- Loratadine, the parent compound of DL, is also available via prescription and over-the counter in the Nordic countries. We think it is somewhat unlikely that patients would switch between DL and loratadine. However, it is possible that some of the time counted as unexposed in the analyses could actually be time exposed to loratadine or over-the-counter DL. Moreover, other non-sedating prescription antihistamines are available in the Nordic countries, and if the effect on the outcomes

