is driven by non-sedating prescription antihistamines in general, rather than the specific effect of desloratadine exposure only, these drugs should be examined to elucidate potential misclassification of exposure. To explore exposure misclassification (i.e., the influence of loratadine and other non-sedating prescription antihistamines on the associations under study), we will conduct supplementary analyses, which will be specified in the statistical analysis plan.

Outcome: Episodes of seizures, SVT, and A-fib/flu

- Seizures, SVT, or A-fib/flu not registered with a relevant diagnosis code in the national patient registers will not be included in the study. However, the completeness of registration is assumed high, since both a procedure for data control of information in the national patient registers is established, and hospitals have an incentive to register patients, as the financing of hospitals is based on the registration of patients treated and procedures performed. If under-recording exists, it would reduce the number of outcomes evaluated, but this under-recording is not likely to be differential (i.e. associated with periods of use or nonuse of DL) and introduce bias.
- The coverage of calendar years in the national patient registers differ between the Nordic countries and may be insufficient to capture the complete history of seizures, SVT, or A-fib/flu at the individual level. Regarding seizures, recurrent seizures would be studied as primary seizures, if first seizure happened before start of registration.
- Truncation is a potential bias in the study meaning that we have no information on seizures, SVT, and A-fib/flu before the start of registration of each of these variables. For Denmark, Finland, and Sweden, information on seizures, SVT, and A-fib/flu is available from 1977, 1967, and 1987, respectively. Thus, the impact of truncation bias on results from these countries is limited. However, information on seizures, SVT, and A-fib/flu in Norway is only available from 2008, which limits the study period of the Norwegian data further and increases the risk of truncation bias.

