- The present study aims at studying incident outcomes occurring in the community setting. To differentiate between incident and prevalent disease, we exclude persons with registered disease before baseline. In addition, we used surrogates of prevalence (i.e., redeemed prescriptions of antiepileptic medicine) to exclude persons with prevalent disease. To capture disease cases emerging in the community setting, we limit ascertainment to those sites of care where incident presentation would be present and use only primary diagnoses of hospitalization, as secondary diagnoses often represent conditions emerging during hospitalization.

Confounders

In the present study, we expect complete information on the central confounders of age, sex, calendar year, country, and seasonality, as these are measured as key variables in the registers and information on these variables has to be entered into the system to establish a record file.

Information on the three confounders of severity of rhinitis, asthmatic status, and chronic urticaria status is challenging to obtain from the nationwide registers for many reasons. First of all, these conditions in general emerge in the primary health care sector where patients normally seek care from their general practitioner for treatment of symptoms. Second, truncation bias may, as with regard to the measures of exposure and outcome, also occur in relation to these three confounders in Norway as the patient register was established in 2008, making the follow-up period rather short. Third, different issues regarding codes and use of drugs for the three conditions have to be realized and discussed to understand the potential impact of residual confounders in the present study. We have discussed these issues with clinical experts and the essence of the discussion is given below.

- Severity of rhinitis is measured as use of immunotherapy and the binary measure of severity of rhinitis will not capture different levels of disease severity. Therefore, we expect the sensitivity of the measure to be rather low and severity of rhinitis to be underreported in the present study. However, we do not expect misclassification of those persons who received immunotherapy, as it is assumed that persons receiving immunotherapy also have severe rhinitis. A quantitative bias analysis examining the impact of misclassification of severity of rhinitis on the results will be performed.

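### Counting any N05BA dispensing as antiepileptic medicine takes first seizures out of the Substudy 2A numerator only, by an amount that varies with each country's prescription look-back

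*Protocol*

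**What the plan says.** Section 7.2.2 excludes from 2A people with a prior seizure or epilepsy diagnosis, or with "prescriptions of antiepileptic medicine before entering the study period, as they have prevalent disease". Prevalent disease is the only reason given there for the drug criterion. The separate reason of high seizure risk is attached in 2A to malignant brain tumour and head trauma. Section 7.9 describes the drug criterion in the same way: "we used surrogates of prevalence (i.e., redeemed prescriptions of antiepileptic medicine) to exclude persons with prevalent disease".

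Annex 6 defines antiepileptic medicine as ATC N03A and N05BA, with no limit by substance, indication or number of dispensings.

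For the denominator, Section 7.7.2 takes NORDCAN counts, "assuming each person in the population on 01 January of each year contributes one person year at risk". Section 7.6 builds person-level populations only for DL users and for people with an outcome, so an excluded person without a seizure cannot be subtracted.

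The result is a primary objective (Section 6), and Section 7.1 plans the analysis by country: "IR of first seizure overall in the general population and stratified by country, sex, and age will be conducted".

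On register starts, Section 7.9 states that "the prescription registers in Denmark and Finland were established in 1995 and 1994, respectively" and that "the prescription registers in Norway and Sweden were established in 2004 and 2005, respectively". Its prescription-register paragraph deals with DL use only. Its statement for Denmark, Finland and Sweden that "the impact of truncation bias on results from these countries is limited" rests on how far back the diagnosis data go.

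**The concern.** The code list is wider than the reason given for it. N05BA lies outside the antiepileptic group N03A, and an anxiolytic dispensing alone is weak evidence of existing seizure disease. Someone with such a dispensing who later has a genuine first seizure is dropped as a prevalent case.

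Because only the numerator is cleaned, each such loss lowers the reported rate. The number lost grows with the years of prescription history available before study start, and these years differ widely between countries. Part of any difference between national rates could then reflect when each prescription register opened. The planned confidence interval would not show this. The data control reports must give reasons for exclusions, but nothing asks for the number due to N05BA alone, so a reader could not judge the size.

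**Working it through.** The plan gives no figure for this effect, so there is none to reproduce.

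**Prescription look-back** (study start in Section 7.2 minus register start in Table 5 and Section 7.9):

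| Country | Register | Study start | Look-back L |
|---|---|---|---|
| Finland | 1994 | 2001 | 7 years |
| Denmark | 1995 | 2001 | 6 years |
| Norway | 2004 | 2008 | 4 years, or 0 |
| Sweden | 2005 | July 2005 | at most 0.5 year |

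The Norwegian range arises because Table 5 lists prescriptions from 2004 but data extraction from 2008, and Section 7.4 says: "The data extraction period refers to the longest period for which data on exclusion variables".

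**Direction.** With a full-population denominator, planned rate = true rate × (1 − f), where f is the share of first seizures in people excluded by N05BA alone. Since f cannot be negative, this component can only lower the rate.

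**Break-even, with no assumption on N05BA use.** Section 5 equates 270,000 Danes with about 5% of the population: 270,000 / 0.05 = 5.4 million. Over 15 years at 40 per 100,000 (the adult rate in Section 7.5.3) this gives 32,400 events. Taking N in the Section 7.7.2 interval as the number of first seizures, the lower limit is exp(−1.96/√32,400) − 1 = −1.08%, or 0.0108 × 32,400 ≈ 350 seizures. At 60 per 100,000: 48,600 events, −0.885%, about 430 seizures. Above these counts the loss exceeds Danish sampling error.

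**Illustration on assumed inputs.** First N05BA dispensing h = 1% to 3% per year, population turnover d = 1% to 4% per year, and equal seizure risk in users and non-users.

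- Loss at study start: s = 1 − exp(−hL).
- Average over T study years: s × (1 − exp(−dT))/(dT).
- The second factor is 0.752 to 0.929 for T = 15, 0.856 to 0.961 for T = 8 and 0.817 to 0.949 for T = 10.5.

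| Country | At start | Period average |
|---|---|---|
| Finland | 6.8–18.9% | 5.1–17.6% |
| Denmark | 5.8–16.5% | 4.4–15.3% |
| Norway, L = 4 | 3.9–11.3% | 3.4–10.9% |
| Norway, L = 0 | 0% | 0% |
| Sweden, L = 0.5 | 0.5–1.5% | 0.4–1.4% |

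With equal true rates, the Sweden/Finland ratio would read (1 − 0.0041)/(1 − 0.0508) = 1.05 up to (1 − 0.0141)/(1 − 0.1759) = 1.20.

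**A second model, at study start.** f = P·RR/(P·RR + 1 − P), where P is the share with any N05BA dispensing in the look-back and RR the seizure rate ratio of users to non-users. For L of at least 1 year, P = 1 − (1 − prevalence) × exp(−new use × (L − 1)). Norway is taken at 4 years and Sweden at 0 (0.5 year in brackets). A true rate of 40 becomes:

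| Assumed prevalence, new use per year, RR | Finland | Denmark | Norway | Sweden |
|---|---|---|---|---|
| 1%, 0.5%, 1 | 38.4 | 38.6 | 39.0 | 40.0 (39.8) |
| 3%, 1%, 2 | 33.6 | 34.3 | 35.6 | 40.0 (38.8) |
| 6%, 2%, 4 | 22.2 | 23.5 | 26.3 | 40.0 (35.6) |

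The spread shows how far the size depends on the inputs. The country order follows from look-back if N05BA use is similar across countries and Norway has its 4 years.

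**Age.** Exclusion needs a dispensing before study start. In Denmark and Finland every child aged 0–4 on 1 January 2006 or later was born after the 2001 start and cannot be excluded this way. Section 7.5.3 puts the highest seizure rates at younger ages (65 and 50 per 100,000 against 40 in adults), which dilutes the all-age loss.

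**The case against.** The strongest reply is that N05BA is not the root cause. Every 2A history exclusion removes cases from the numerator only and rests on unequal look-back. Prior head trauma and malignant brain tumour do the same, with patient registers starting in 1967, 1977, 1987 and 2008. Narrowing the drug list would not make the country rates comparable. That stands. What N05BA adds is a group excluded as diseased without evidence of seizure disease.

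The size is also open to attack. All the percentages rest on assumed use. The illustration does not subtract people who would be excluded anyway through N03A or a diagnosis, and it ignores age. The break-even is a low bar with so many events. All of this stands, so the figures are illustrations and not estimates.

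Annex 6 lists codes proposed by clinicians, and some N05BA use may mark real seizure disease. That is a reason to keep the list in the main analysis and to ask the clinicians about clobazam. It does not justify treating every N05BA user as prevalent.

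A reader might infer that the published 2A rates will be too low overall. The documents do not support this. Norway has no diagnosis history before its 2008 study start, so prevalent cases can enter as first seizures and push that rate up. Section 7.9 acknowledges that recurrent seizures may be counted as first and that Norway is more exposed to truncation.

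**Conclusion.** The concern holds for the N05BA component of the 2A rate. The exclusion is wider than its stated reason, it acts on the numerator alone, and it biases the adult rate downward by an amount tied to prescription look-back. The effect is near zero in young children and small or nil in Sweden. Section 7.9 does not disclose it.

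The direction of this component follows from the documents, given the ATC meaning of N05BA, which Annex 6 does not spell out. Its size does not, and neither does the net direction of any country's rate.

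A reader might also infer that the 2B rate ratio is biased. That is not shown. In 2B, Section 7.2.2 gives high seizure risk as a further reason for the exclusion, the comparison is within the DL cohort, and the seizure DAG discussion in Annex 8 decided against including use of other drugs. The cost in power is modest: with the Annex 7 formula and Table 6 inputs for age 65 and over, the minimum detectable ratio is 1.68 (stated as 1.7) and becomes 1.72, 1.78 or 1.84 if 10%, 20% or 30% of the cohort is lost. No change to 2B follows.

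**What to change.** - Keep the Annex 6 list as the main 2A analysis. Section 5 says P205 repeats the P203 methods apart from dropping the secondary analyses, so comparability matters.
- Add one 2A sensitivity analysis that limits the drug exclusion to N03A, plus clobazam (N05BA09) if the clinicians agree. Show it beside the main rates by country and age.
- Report by country the number of 2A first seizures removed by N05BA alone.
- State each country's prescription look-back for this exclusion, including whether 2004 or 2008 applies in Norway, and name it in Section 7.9 as a limit on comparing countries.

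The cost is one shorter code list, one more set of rates and one count per country, from prescription data the exclusion already needs. The main result does not change. The downside is that the narrow list may readmit a few prevalent cases treated only with a benzodiazepine, and the count removed by N05BA alone limits how many these can be. The change does not cure the denominator mismatch shared by the other 2A exclusions, and the report should say so.
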